3. STUDY OUTCOMES

3a. Primary outcomes

Aim 2: Stepped-wedge randomized controlled trial (RCT)

The primary outcome for this study is **adolescent retention in HIV care**, defined as:

 Return for 1st follow-up visit after first enrollment visit OR return for follow-up visit after a 're-engagement visit' among adolescents who had previously been lost to follow-up (LTFU) • Retention in care for ANY follow-up visit within 3 months among adolescents currently enrolled in HIV care (which can be referred to as "actively enrolled")

Description:

First follow-up visit after enrollment visit: The number and proportion of adolescents who return to clinic within 3 months of an enrollment visit

Follow-up visit after re-engagement in care among LTFU adolescents: Lost to follow-up is defined as no clinic record for at least 3 months, and no record of death or transfer to another facility. Among adolescents who return to clinic after LTFU, we will collect the number and proportion of adolescents who return for a subsequent visit within 3 months.

Return for follow-up among those currently enrolled in care: To evaluate whether the SPEED intervention may result in better adherence to visit schedule among adolescents currently enrolled in HIV care (i.e. not newly enrolled or previously LTFU), we will also measure return for any follow-up visit within 3 and 6 months.

3b. Secondary outcomes:

Aim 1: Pilot testing of case scripts and establishment of competency

- Final case scripts
- Numeric scores on HCW checklist
- Proportion of HCWs with pass/fail scores
- Numeric scores on actor feedback checklists
- Numeric scores on HCW satisfaction survey
- Numeric scores on HCW self-rated competency survey

Aim 2: Stepped-wedge randomized controlled trial

In addition to the primary outcomes, the RCT will have several secondary outcomes, summarized in in Table 1:

Analyses of *process outcomes* to understand intervention mechanism will include:

- Pre/post-measures of HCW and patient satisfaction
- Pre/post-measures of HCW competency scores
- Associations between HCW competency scores and care outcomes
- Associations between HCW competency scores and adolescent satisfaction outcomes

• Exit interviews in a purposeful sample of HCW participants at the end of the trial

Table 1. Summary of process outcomes, exploratory outcomes, and indicators in Aim2 RCT

Process Outcomes	Indicator	Source
HCW competency	Mean HCW scores per clinic	Faculty graded scores
		Exit interviews

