part of the intervention. The study team will meet with clinic leadership and managers
first to gain access to providers. A study staff member will then approach those providers
to invite them to learn more about the study.

Within participating clinics, all clinical providers who have contact with adolescent clients will be approached for participation. Eligible providers at that facility will give informed consent (see Section 13). Eligible providers at that facility will give informed consent. We anticipate an average of 10 HCWs per site, depending on clinic size.

 Adolescents attending clinics: A clinical staff member will be instructed by our Study Team to refer consecutively, all adolescents seeking HIV care on a given day, to the Study Team member. This Team member will be at each clinic to invite adolescents to complete an anonymous, tablet-based survey to assess satisfaction with their counseling or treatment encounter. We will track numbers of adolescents referred compared to total adolescent patients, and reasons for not referring to identify any differences in referrals by time of day or day of week.

We expect to enroll at least 5 adolescents per clinic per time period and up to 20, depending on clinic volume (20 adolescents X 5 time periods X 24 clinics = up to 2,400). A Study Team member will be at each clinic for 1-3 days for recruitment.

Retention strategies for HCWs and adolescents: While the intervention targets health facilities, we will track individual providers to assess retention in service provision at clinical intervention sites, using a facility survey to monitor staff turnover. In addition, provider names and phone numbers will be recorded, and we will assess the provider's continued employment at the sites, as well as any cross-over to other study sites, at each measurement time point. Adolescent surveys will be cross-sectional at each time point. Accordingly, there is no need for a retention strategy for this group.

Cost Effectiveness Analysis and Cost Utility Analysis (CUA)

No participants will be recruited specifically for this analysis. Questions on direct and indirect costs, as well as clinic and hospital visits, to the adolescents will be included in the adolescent satisfaction survey (Appendices). Other cost data will be drawn from program data, the literature, and our prior studies.

5f. Randomization procedures

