Data from the completed faculty checklists will be used to establish competency scores. Participants, faculty experts, and actors will be asked to provide qualitative feedback on the checklist indicators. Inter-rater reliability of the faculty checklist will be determined using Cohen's kappa. We will assess correlation of checklist variables and utilize principal component analysis to reduce the number of variables, using a scree test method to plot eigenvalues. Pass/fail cutoff scores will utilize relative and absolute standard-setting processes [33]. In relative processes, initial pass/fail determinations will depend on the performance of the cohort, such that all scoring less than 1 standard deviation below the mean receives a fail. Relative standards are useful with new trainings where there is no prior performance data. Subsequently we will explore standard-setting using an iterative combination of the Angoff item-based method and the Hofstee whole-test method. The Angoff method establishes the probability of a borderline student to accomplish each item on the checklist. The sum of probabilities across items is then equal to a passing score. A team review process is convened in which reviewers discuss outlier ratings, assess performance data after pilot testing, and revision of ratings if necessary. The Hofstee whole-test method combines normative and absolute judgments, in that checklist reviewers make four determinations: the minimum and maximum acceptable passing scores. and the minimum and maximum proportions of students failing. A final cut-off determination will be made by averaging the Hofstee and Angoff scores.

Stepped-Wedge Randomized Controlled Trial

The primary analysis will be an intent-to-treat (ITT) analysis, assuming that adolescents who receive care at clinics after the SPEED training will be 'exposed' to HCWs trained in the SPEED intervention until the end of the study.

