A CONSORT diagram, adapted for a stepped-wedge design [34] will be used to show the number of HCW-participants within clusters and flow of randomized stepped wedge clusters though the five time periods. We will report the number of clinics selected for inclusion, assignment to intervention or control at each time period, and the number of HCWs trained at each facility. We will report number of excluded clusters and any reasons for exclusion. No replacement will be used. Facility-specific information – adolescent patient volume, number of HCWs and presence of any adolescent-specific service (peer groups, clinics etc.) prior to the intervention – will be grouped by clinic and recorded. Baseline values of primary and process outcomes, and socio-demographic characteristics of adolescents and HCWs will be presented in a descriptive table.

We will use generalized linear mixed models (GLMM), which are more efficient than paired ttests and linear mixed models (LMMs) in the analysis of cluster RCTs when the size of clusters is unequal [32] to compare the probability of an adolescent returning to clinic after enrollment visit OR second visit after >3 months LTFU between the intervention and control periods [35]. To estimate the effect of the intervention (*Xij*) on the individual level, we will use a GLMM model with a Poisson distribution and robust standard errors, allowing for random effects for clusters (*ui*) and fixed effects for time (*j*). This approach models individual level outcomes, adjusts for temporal trends and accounts for correlation of outcomes within a cluster (clinic). We will estimate adjusted risk ratios (ARR), adjusted risk differences (ARDs) and 95% confidence intervals at the 5% significance level (two-sided). Adjusted risk ratios will be estimated for secondary outcomes: initiating and adherent to ART (≥80% in the dosing period by pharmacy records), 12-month retention in care; viral suppression (<100 copies/ml, <1000 copies/ml), and referred for ancillary services (family planning and TB screening). Models will be adjusted for facility type, patient volume, and exposure to prior adolescent health interventions (c).

The equation for a generic model is: $Y_{ijk} = \beta_0 + \beta j_{time} + \beta_{effect} X_{ij} + \beta c X ij$, $ui + \varepsilon ij$

- Analyses of process outcomes to understand intervention mechanisms will include:
 - Mean HCW competency (passing score proportion per clinic) before and after the intervention

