 - Association between mean HCW competency scores per facility and adolescent satisfaction scores
 - Associations between mean adolescent satisfaction scores and 1) retention in care (binary), 2) referral to APS services (binary), 3) ART adherence (binary or mean percent), and 4) viral suppression (binary) comparing the exposed and unexposed periods.
- Evaluation of temporal trends: Temporal trends that change over time (e.g. introduction of new HIV treatment guidelines, COVID-19) and potentially impact study outcomes can lead to a biased effect estimate in a stepped-wedge trial design [34]. To assess this possibility, we will repeat the primary analyses including an interaction term between a time indicator (e.g. coded as 'pre' versus 'post' policy/program change) and the variable for the main effect. A p-value for the interaction <0.1 will be evidence of interaction. We will report these results in a separate table showing any differences in intervention effect by this temporal change.

- Lag effects of SPEED intervention: Because the effect of the intervention may not be immediate or it may diminish over time, we will evaluate these possibilities in two ways. HCWs may take time to put skills they learned in the training into practice. In addition, trained HCWs may decrease or stop using these new skills. Intervention lag will be modeled by re-coding the first month after the intervention as a control period, as recommended by Davey *et al.* [34]. We will model the reduction of the intervention effect over time by using a fractional term for the coefficient of primary effect estimate, which will have a value of 1 (assumes 100% exposure) and get smaller at each time step (e.g. 75%, 50%, 25%).
- Qualitative analysis of exit interviews: Qualitative data from the HCW exit interviews will be coded in Atlas.ti. Data will be analyzed by two reviewers using thematic analysis according to the interview guide. These results will be utilized to complement results from the structured HCW satisfaction surveys.

Cost-effectiveness Analysis (CEA) and Cost Utility Analysis (CUA)

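### Health-worker competency is a mean score in Table 1 but a pass proportion in the before/after analysis of section 12c; the mean score should be used throughout

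*Combined protocol and SAP*

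**What the plan says.** The competency outcome of the Aim 2 trial appears in four places.

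- Section 3b, list of process outcomes: "Pre/post-measures of HCW competency scores".
- Section 3b, Table 1: the indicator is "Mean HCW scores per clinic", with the source given as "Faculty graded scores" (exit interviews are also listed).
- Section 12c, first process-outcome bullet, the before/after comparison: "Mean HCW competency (passing score proportion per clinic".
- Section 12c, next bullet: "Association between mean HCW competency scores per facility and adolescent satisfaction scores".

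The pass/fail line itself comes from the pilot phase. Section 12c starts from a rule relative to the cohort, under which "all scoring less than 1 standard deviation below the mean receives a fail" (I read this as scores below the mean minus 1 SD). It then states: "A final cut-off determination will be made by averaging the Hofstee and Angoff scores". In section 3b the proportion passing or failing is listed only for Aim 1, alongside numeric scores, and not for Aim 2.

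On numbers, Table 2 allows up to 10 HCWs in each of 24 clinics, and section 5e says: "We anticipate an average of 10 HCWs per site, depending on clinic size".

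**The concern.** Three of the four places treat competency as a numeric score. The fourth, which is the only one that specifies the before/after analysis, replaces it with a pass proportion while still calling it a mean. The two summaries can disagree. The pass proportion ignores any movement that does not cross the line, and its value depends on where the line is drawn. With both definitions in the plan and no rule for choosing, the reported summary could be picked after the results are known.

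Competency is the first step in the mechanism that the process analyses are meant to examine, from training to skill to patient satisfaction to retention. A less precise measure of that step, defined differently from the one used in the next step, makes the chain harder to read.

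**Working it through.** **Plan's own figure.** 24 clinics × 10 HCWs = 240, as in Table 2. The documents give no power or precision figure for competency.

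**Information kept by pass/fail.** Assume roughly normal scores and a small shift in the mean. With a cut-off c SDs from the mean, the efficiency of the pass proportion relative to the mean score is

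ARE = φ(c)² / [Φ(c)(1 − Φ(c))].

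At c = −1: φ² = 0.0585 and Φ(1 − Φ) = 0.841 × 0.159 = 0.1335, so ARE = 0.0585 / 0.1335 = 0.439.

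| Cut-off relative to the mean | Pass rate | Information kept | Loss | Worth of 10 pass/fail results, in scores |
|---|---|---|---|---|
| At the mean | 50% | 0.637 | 36% | 6.4 |
| −0.5 SD | 69% | 0.581 | 42% | 5.8 |
| −1 SD (provisional pilot rule) | 84% | 0.439 | 56% | 4.4 |
| −1.5 SD | 93% | 0.269 | 73% | 2.7 |

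The loss passes one half at about −0.81 SD (pass rate 79%). At −1 SD, 1/0.439 = 2.28 times as many HCWs are needed for the same power, and the detectable difference is √2.28 = 1.51 times as large.

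**Other score shapes at the mean minus 1 SD.** Loss is 50% for uniform scores, 60% for logistic, 61% for t with 5 df, and 71% to 74% for two left-skewed beta shapes.

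**Larger shifts.** These are sample sizes per group for two independent groups, two-sided α 0.05 and 80% power. The α is the one in section 12c. The power is borrowed from the retention calculation in section 12a, and the shifts are assumed.

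- Cut-off at −1 SD of the before scores: for a 0.2 SD shift, 393 by means against 975 by pass/fail (efficiency 0.40); for 0.5 SD, 63 against 185 (0.34).
- Cut-off at −1 SD of the after scores: for 0.2 SD, 393 against 836 (0.47); for 0.5 SD, 63 against 124 (0.51); for 1.0 SD, 16 against 29 (0.55). The loss is about 45% to 53%.

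**Dependence on the cut-off.** Take one and the same gain of 0.5 SD. With the line at the before mean, the pass rate goes from 50.0% to 69.1% (19 points). With the line 0.5 SD below it, from 69.1% to 84.1% (15 points). With the line 1 SD below it, from 84.1% to 93.3% (9 points). The gain in mean score is 0.5 SD in all three cases.

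**Availability of a before value.** Section 11 limits the faculty checklist to the training and has the final score assigned once the training is over. It mentions no faculty score before training. The self-rated competency survey in section 11 is a different instrument, and its first stated use is also after training.

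**The case against.** The strongest reply is that this is one loosely worded bullet for a process outcome. The plan keeps the numeric score elsewhere, its process list need not be exhaustive, and a pass/fail standard is a deliberate product of Aim 1 that trainers can interpret directly. That stands as a reason to keep reporting the pass proportion. It does not settle which summary governs the before/after comparison.

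A reader might infer more than the documents support, in three ways.

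- **That the plan throws away over half of the information.** The 56% belongs to the mean-minus-1-SD rule, which is provisional and gives way to the averaged Angoff/Hofstee value. Section 7a places standard-setting in the pilot phase, so the initial rule is not shown to govern any trial analysis. If the final line lies closer to the mean than about 0.81 SD, the loss is under half.
- **That the pass proportion will sit near its ceiling and hide real gains.** At an 84% pass rate, a clinic of 10 would have about 1.6 fails, and 18% of clinics would show all passing by chance. But that rate describes the cohort on which the line is set, here 10 pilot HCWs at one hospital who took the training. Nothing gives the pass rate of untrained trial HCWs. Even with the line at −1 SD of the before scores, 240 per group gives 80% power for a shift of about 0.43 SD by pass/fail, against 0.26 SD by means (independent groups, clustering ignored). Only small to moderate gains are at risk.
- **That moving to the mean score needs no new data.** This is secure for the post-training scores only, because no pre-training faculty score is described.

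The efficiency formula also treats the comparison as two independent samples, while the bullet compares before with after within clinics. The figures are therefore a guide to relative precision and not a power calculation for this analysis.

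**Conclusion.** The inconsistency is plain in the text, and the summary in the before/after bullet is the weaker of the two. Under normal scores and a small shift, the loss is at least 36% wherever the line falls. It is 42% at −0.5 SD and 56% at −1 SD. Which of these applies cannot be known, because the documents do not locate the final cut-off. The assumptions are score shape, size of shift and cut-off position; the alternatives above show how far each moves the result.

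The pass proportion also carries the choice of cut-off into the result, and the mean score does not. The missing before value is a gap under either summary.

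The point is minor. It concerns a process outcome only and leaves the primary retention analysis, its sample size and its power as they are.

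**What to change.** In section 12c, change the before/after bullet to the mean faculty score, matching Table 1 and the satisfaction association. Analyse it at HCW level with a random effect for clinic. Report the proportion passing at the final cut-off descriptively.

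In the same line, state which already planned score serves as the before value. If none does, describe the faculty score as a post-training measure and drop the before/after comparison for it. Use the same numeric score in every competency association listed in sections 3b and 12c.

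The cost is a line or two of analysis-plan text. Post-training scores are already to be stored for each HCW, so that part needs no new data. Whether a before/after comparison is possible depends on the answer about the before value.

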Each intervention wave will train HCWs from 6 clinics. At the beginning of training, participant HCWs will fill out social demographic forms. They will then complete the training sessions, including didactic lessons, videotaped encounters, and debriefing sessions. Feedback and scoring will be provided using SP checklists for emotional responses, faculty checklist for technical skill, and group discussion for peer support. Intervention waves will be repeated until all sites have received the training (see timeline).

7c. Procedures for training interventionists and monitoring intervention fidelity

A consultant expert will train the SP actors on procedures for conducting the encounters and giving feedback. Intervention fidelity (fidelity of the actors to their assigned cases) will be monitored during the trial through period assessments of actor fidelity. Study team members will review a random sample of video-taped encounters in each intervention wave, and rate actor fidelity according to a standard actor fidelity checklist (see Appendices). In addition, the trainer will provide periodic refresher trainings for the actors during the trial.

7d. Assessment of participant compliance with study intervention

Once the training is completed, we will regularly conduct facility surveys to monitor turn-over of SPEED trained HCWs, changes in clinic policies and procedures, and other facility-level factors that could affect intervention fidelity.

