11. DATA COLLECTION

All data collection tools submitted with this application can be found in the Appendices.

Data sources for HCW participants

- Audio-visual recordings: Video-recordings, locally recorded on a web-camera and uploaded to the SPEED learning management system (LMS), will be made of each HCW-SP interaction for training, scoring, and debriefing/feedback purposes in the pilot and in the RCT. The LMS will utilize Canvas software, a program available only to the Study Team and HCW participants. Each HCW will have a study ID number assigned to them and will log in to the LMS using a user name and private password.
- Surveys:
 - Actor feedback checklist (used in training only): Actors will complete an actor feedback checklist and review it with each HCW during the training.
 - Faculty checklist (used in training only): Faculty experts will review the videos and complete a faculty checklist with a final competency score for each HCW immediately after the training. These scores will be stored with each user record.
 - HCW sociodemographic and satisfaction survey: HCW participants will complete the sociodemographic and satisfaction questions at baseline and in the SPEED training.
 - HCW self-rated competency: HCW participants will complete the competency survey immediately after their training and at the end of each wave to assess perceived competency to care for adolescent patients. The survey will be repeated to assess changes in competency over time during the trial. The final survey will be conducted by telephone due to COVID-19.
 - Exit interviews: A purposeful sample of HCW participants from each wave will take part in one semi-structured exit interview each at the end of the RCT to better understand barriers and facilitators to applying the skills they learned in the SPEED intervention to their routine practice. The interview will follow a structured interview guide.
 - Facility survey: This survey will be administered to a health facility representative at baseline and at the end of each wave of the RCT to capture facility characteristics, including turn-over of SPEED-trained HCWs, patient volume, and any relevant changes in HIV policies and procedures.
- Program records:
 - *Cost data:* Direct and indirect cost data for the CEA/CUA analyses will be obtained from clinic program data (e.g. HCW salaries from employment records)

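### The planned check for bias from policy or programme changes tests effect modification; it neither reliably detects nor removes a shift from changes that reach clinics at different times

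*Combined protocol and SAP*

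**What the plan says.** The temporal-trends paragraph of Section 12c names new treatment guidelines and COVID-19 as examples of changes that "can lead to a biased effect estimate in a stepped-wedge trial design". Its response is: "To assess this possibility, we will repeat the primary analyses including an interaction term between a time indicator". The coding of the indicator is given only as an example ("e.g. coded as 'pre' versus 'post' policy/program change) and the variable for the main effect"). The decision rule is "A p-value for the interaction <0.1 will be evidence of interaction", and the output is a separate table "showing any differences in intervention effect by this temporal change".

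The primary model in the same section is a Poisson mixed model with robust standard errors, a random effect per clinic and time effects shared by all clinics. The listed covariates are facility type, patient volume and exposure to earlier adolescent interventions. None codes a policy or programme change during the trial.

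Section 11 schedules a facility survey at baseline and at the end of each wave, covering "patient volume, and any relevant changes in HIV policies and procedures". Section 7d adds regular surveys after training to follow "changes in clinic policies and procedures, and other facility-level factors that could affect intervention fidelity". No analysis in Section 12 uses these answers. Table 2 bars concurrent adolescent interventions as an inclusion criterion for clinics, and Section 8 puts the trial at about three years.

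**The concern.** The question posed is whether outside changes shift the estimate. The test chosen asks whether the training effect differs before and after a change. These are different questions. A change that reaches all clinics together, with the same effect in each, is taken out by the period effects. A change that starts in different clinics at different times is not, and an interaction with training does not adjust for it.

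Two things are at stake. A non-significant interaction may be taken as reassurance about bias that the test cannot give. And the survey information that could address the question would be collected but left out of the analysis.

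**Working it through.** **Inputs.** From Sections 8 and 12a: 24 clinics, 4 waves of 6, 5 periods, control return 75%, difference 15 points, coefficient of variation 0.25, two-sided α 0.05, 6 or 40 records per clinic-period. Assumed, because the documents give no figure: an outside change adds 10 points to return. All shifts scale linearly with this. The calculations use a linear approximation to the planned Poisson model.

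**1. The plan's own figures.** The Hussey-Hughes variance is Iσ²(σ²+Tτ²) / [(IU−W)σ² + (U²+ITU−TW−IV)τ²], with U=60, W=1,080, V=180. Take mean rate 0.825, τ = 0.25×0.75 = 0.1875 and σ² = 0.825×0.175/6 = 0.02406.

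- Numerator: 24×0.02406×(0.02406+5×0.03516) = 0.1154.
- Denominator: 360×0.02406 + 1,080×0.03516 = 46.63.
- SE = √(0.1154/46.63) = 0.0497, and power = Φ(0.15/0.0497−1.96) ≈ 85%.

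Five records per cell give about 79%. With 20 clinics, 7 per cell give about 84%. Forty per cell give over 99%. The stated 720 and 700 records and the >99% power are reproduced, so the layout is right. At 40 per cell the SE is 0.0199.

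**2. Where a shift can come from.** Between-clinic variance is large, so the estimate is close to the within-clinic one. Centre the training indicator by clinic and by period:

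| Wave | P1 | P2 | P3 | P4 | P5 |
|---|---|---|---|---|---|
| 1 | −0.30 | 0.45 | 0.20 | −0.05 | −0.30 |
| 2 | −0.10 | −0.35 | 0.40 | 0.15 | −0.10 |
| 3 | 0.10 | −0.15 | −0.40 | 0.35 | 0.10 |
| 4 | 0.30 | 0.05 | −0.20 | −0.45 | 0.30 |

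The sum over trained cells is 0.30+0.45+0.45+0.30 = 1.50. The shift is the outside effect × (sum over cells with the change) / 1.50.

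- *Common date:* every column sums to zero, so the shift is 0.
- *Arrival tied to wave* (waves 1–2 at period 3, waves 3–4 at period 5): −0.15+0.45+0.10+0.30 = 0.70, so 10×0.70/1.50 = +4.7 points. The full weighted calculation at 40 per cell also gives +4.7.
- *Milder imbalance* (4 of 6 clinics early in waves 1–2, 2 of 6 in waves 3–4): +1.6 points.

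**3. Arrival unrelated to wave.** Random start steps in 8, 12 or 24 clinics, 2,000 draws each:

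| | 8 clinics | 12 clinics | 24 clinics |
|---|---|---|---|
| SD of shift, 6 per cell (points) | 0.81 | 0.96 | 1.29 |
| SD of shift, 40 per cell (points) | 0.77 | 0.95 | 1.26 |
| Variance ratio, adjusted/unadjusted, 6 per cell | 0.982 | 0.975 | 0.955 |
| Variance ratio, adjusted/unadjusted, 40 per cell | 0.876 | 0.823 | 0.725 |

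The mean shift is zero. The widest 95% range is 1.96×1.29 = ±2.5 points. For an outside effect of 5 or 15 points it would be about ±1.3 or ±3.8. A clinic-by-period main effect raises the model SE at 6 per cell only from 0.0497 to 0.0502.

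**4. What the planned interaction does.**

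- *Random staggered arrival, date at period 3, 12 or 24 clinics:* p<0.1 in 10.5–14% of cases, against a nominal 10%.
- *Wave-tied pattern at 40 per cell, variance at the 75% control rate (SE 2.26 points), true training effect 0:* the primary model rejects with probability Φ(4.72/2.26−1.96) ≈ 55%. With the date at period 3, the interaction is 8.8 points (SE 4.1) and reaches p<0.1 in 69%. The two effects it would tabulate are −1.4 and +7.4 points. With the date at period 4, p<0.1 falls to 14%. A clinic-by-period main effect gives zero bias, with SE 2.7 points.
- *Last period:* all clinics are trained, so training × last period equals the period-5 indicator. The design has rank 6 of 7 and the term cannot be estimated. A date at the first training step fails likewise, since no clinic is trained before it.
- *Clinic-specific coding without its own main effect:* p<0.1 in 67–99% of the staggered set-ups, although the training effect was constant.

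**The case against.** The strongest reply is that randomisation already protects the estimate. Clinics are randomised to wave, stratified by region and size (Section 5f), so a change unrelated to wave has zero expected effect and what remains is noise. The plan specifies robust standard errors. In a simulation of random arrival that assumed clustering by clinic (which the text does not state), they held type I error at 5.3–5.7% with 6 per cell and 4.3–5.5% with 40; model-based errors reached 9.1%. This stands. Under random arrival the gain from the extra model is precision, and at 6 per cell that gain is only 2–5%. Robust errors do not help if arrival follows wave, but nothing in the documents points to such a link.

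Several stronger readings are tempting, and the documents do not support them:

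- *That the interaction can never detect a shift.* It sometimes reacts, in up to 69% of cases in the most extreme pattern, but a reader would take that as effect modification.
- *That the plan fixes one calendar date.* The coding is only an example. A clinic-specific indicator entered with its main effect would remove the shift where it can be estimated, but the text commits only to the interaction.
- *That dates of change are recorded.* The surveys capture changes by wave; dates are not mentioned. Nor is it stated that a partner's adolescent programme would be captured.
- *That p>0.1 is declared to exclude bias.* The plan says only what p<0.1 means.

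The interaction also has its own value, since an effect that varies over calendar time matters to a model that assumes a constant one.

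**Conclusion.** The mismatch between the stated purpose and the test is plain from the text, and it is worth correcting. It does not show that the trial's estimate is biased, and it does not invalidate the primary model. Nor do the documents support calling staggered outside changes the main threat to the trial.

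For arrival unrelated to wave, the expected bias is zero. A single realised allocation can be off by up to about ±2.5 points per assumed 10-point outside effect, against a 15-point target. The variance cost is about 2–5% at 6 per cell and 12–28% at 40, which Section 12a calls the optimal scenario. Systematic bias (+4.7 points in the pattern worked through) needs arrival associated with wave. That shift would be about two standard errors at 40 per cell (4.7/2.3) but about one at 6 per cell (4.7/5.0). All sizes rest on the assumed 10 points and the linear approximation; the removal of the shift also assumes correct dating and one common effect of the change.

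**What to change.** In the temporal-trends paragraph of Section 12c:

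- Keep the interaction, but label it as a test of effect modification.
- State that the period effects handle changes common to all clinics.
- Note when the interaction cannot be estimated, in particular for a change confined to the last period.
- Add one sensitivity version of the primary model, with a clinic-by-period main-effect indicator for each externally imposed policy or programme change. Code it by wave from the facility survey, asking for the date of change where possible. Classify changes without sight of retention data. Report the training effect with and without the indicators.

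Restricting the indicators to externally imposed changes avoids adjusting away consequences of the training. The cost is SAP wording, coding of survey items already planned and one extra model; the primary analysis and sample size do not change. The downsides are some judgement in classing a change as external, and less benefit if changes are misdated. With half the clinics misdated by one period (40 per cell, 24 clinics), the variance gain fell from about 27% to about 10%.
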